5.5.2 Restarting Nivolumab in Patients Treated with Corticosteroids

Grade 2 events must resolve to \leq Grade 1 before considering retreatment.

All patients treated with steroids for grade 2 events should have nivolumab withheld until resolution to \leq Grade 1 for at least 2 weeks following complete removal from steroid treatment except for maintenance replacement doses for adrenal insufficiency (preferably no greater than 10mg prednisone equivalent daily).

All patients treated with steroids for grade ≥ 3 events should have nivolumab discontinued.

Patients with grade 3 thyroiditis and skin rash may continue therapy, as for grade 2 events with resolution and stable replacement treatment.

Patients with hepatitis, pancreatitis, pneumonitis, and colitis are at risk for exacerbation with retreatment if there is residual inflammation and should resolve to Grade 0 or baseline before retreatment. Baseline can mean the initial grade i.e. grade <1 where permitted on study.

Patients with thyroiditis or hypopituitarism who are stable as above may be restarted with replacement hormones including thyroid hormone and physiologic doses only of corticosteroids. Please note that grading and for hypophysitis with symptoms of headache, visual or neurologic changes or radiologic evidence of pituitary enlargement and other CNS events such as aseptic meningitis or encephalitis should be considered grade 3 events.

New immune related events or exacerbation of existing events during steroid treatment or taper suggest the presence of ongoing immune activation and should require permanent discontinuation of nivolumab.

A patient who is treated with steroids, evaluated, and found to not have an autoimmune or inflammatory event requiring steroid treatment, may be restarted if asymptomatic off steroids for 2 weeks and other restarting criteria are met.

Prior to starting corticosteroids or hormone replacement for any reason, appropriate endocrine testing including cortisol, ACTH, TSH and T4 must be drawn if clinically feasible to document baseline function and distinguish the pituitary from peripheral organ dysfunction and later from steroid (or thyroid) treatment associated ACTH (or TSH) suppression. Steroids should be started prior to obtaining results based on clinical indications.

5.6 Treatment of Nivolumab-Related Infusion Reactions

Since nivolumab contains only human immunoglobulin protein sequences, it is unlikely to be immunogenic and induce infusion or hypersensitivity reactions. However, if such a reaction were to occur, it might manifest with fever, chills, rigors, headache, rash, urticaria, angioedema, pruritis, arthralgias, hypo- or hypertension, bronchospasm, or other symptoms.

All Grade 3 or 4 infusion reactions should be reported as an SAE if criteria are met. Infusion reactions should be graded according to NCI CTCAE version 4.0 guidelines.

Treatment recommendations are provided below and may be modified based on local treatment standards and guidelines as medically appropriate:

5.6.1 For Grade 1 Symptoms

(Mild reaction; infusion interruption not indicated; intervention not indicated)

Remain at bedside and monitor subject until recovery from symptoms. Infusion rate may be slowed. If the infusion is interrupted, then restart the infusion at 50% of the original infusion

rate when symptoms resolve; if no further complications ensue after 30 minutes, the rate may be increased to 100% of the original infusion rate. Monitor patient closely.

The following prophylactic premedications are recommended for future infusions: diphenhydramine 50 mg (or equivalent) and/or paracetamol 325 to 1000 mg (acetaminophen) at least 30 minutes before additional nivolumab administrations, slowing infusion rate as above.

5.6.2 For Grade 2 Symptoms

(Moderate reaction requires therapy or infusion interruption but responds promptly to symptomatic treatment [e.g., antihistamines, non-steroidal anti-inflammatory drugs, narcotics, corticosteroids, bronchodilators, IV fluids]; close observation for recurrence and treatment medications may need to be continued for 24-48 hours).

Stop the nivolumab infusion, begin an IV infusion of normal saline, and treat the subject with diphenhydramine 50 mg IV (or equivalent) and/or paracetamol 325 to 1000 mg (acetaminophen); remain at bedside and monitor patient until resolution of symptoms. Corticosteroid or bronchodilator therapy may also be administered as appropriate. If the infusion is interrupted, then restart the infusion at 50% of the original infusion rate when symptoms resolve; if no further complications ensue after 30 minutes, the rate may be increased to 100% of the original infusion rate. Monitor patient closely. If symptoms recur, then no further nivolumab will be administered at that visit. Administer diphenhydramine 50 mg IV, and remain at bedside and monitor the patient until resolution of symptoms. The amount of study drug infused must be recorded on the electronic case report form (eCRF). The following prophylactic premedications are recommended for future infusions: diphenhydramine 50 mg (or equivalent) and (acetaminophen) (or paracetamol) 325 to 1000 mg should be administered at least 30 minutes before additional nivolumab administrations. If necessary, corticosteroids (recommended dose: up to 25 mg of IV hydrocortisone or equivalent) may be used.

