5.3 Duration of Therapy and Criteria for Study Discontinuation

In the absence of treatment delays due to adverse event(s), treatment may continue until one of the following criteria applies:

- Disease progression (unless the investigator judges that the patient is eligible for continuing beyond progression as stated in section 5.7),
- Intercurrent illness that prevents further administration of treatment,
- Patient decides to withdraw from the study, or
- General or specific changes in the patient's condition render the patient unacceptable for further treatment in the judgment of the investigator.
- Unacceptable adverse event(s) which include the following (see also section 6 and specific algorithms in Appendix C):
 - a) Any grade 4 events except as noted in item 'h' below.
 - b) Grade 3 drug-related autoimmune or inflammatory events including uveitis, pneumonitis, diarrhea, colitis, neurologic adverse events, hypersensitivity reaction, or infusion reaction of any duration requires discontinuation except as noted in item 'h' below:
 - c) Any grade 2 drug-related uveitis or eye pain or blurred vision that does not respond to topical therapy and does not improve to Grade 1 severity within the

re-treatment period OR requires systemic treatment.

- d) Patients requiring $> \text{two}$ dose delays for the same type of event (of grade 2 severity or above) should go off protocol therapy, unless the study doctor thinks that it is in the patient's best interest to remain in the study. The study doctor should also consult the Principal Investigator before continuing study treatment.
- e) Any adverse event, laboratory abnormality, or intercurrent illness which, in the judgment of the investigator, presents a substantial clinical risk to the subject with continued study drug dosing
- f) Tumor assessments should continue as per protocol even if dosing is interrupted. Any patients who require additional immune suppressive treatment beyond steroids should go off study treatment
- g) Any dosing interruption lasting > 6 weeks, with the following exceptions:

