5.6.3 For Grade 3 or Grade 4 Symptoms

(Severe reaction), Grade 3 symptoms: prolonged [i.e., not rapidly responsive to symptomatic medication and/or brief interruption of infusion]; recurrence of symptoms following initial improvement; hospitalization indicated for other clinical sequelae [e.g., renal impairment, pulmonary infiltrates]). Grade 4 symptoms: (life threatening; pressor or ventilator support indicated).

Immediately discontinue infusion of nivolumab. Begin an IV infusion of normal saline, and treat the subject as follows. Recommend bronchodilators, epinephrine 0.2 to 1 mg of a 1:1,000 solution for subcutaneous administration or 0.1 to 0.25 mg of a 1:10,000 solution injected slowly for IV administration, and/or diphenhydramine 50 mg IV with methylprednisolone 100 mg IV (or equivalent), as needed. Patient should be monitored until the investigator is comfortable that the symptoms will not recur. Nivolumab will be permanently discontinued. Investigators should follow their institutional guidelines for the treatment of anaphylaxis. Remain at bedside and monitor patient until recovery from symptoms. In the case of late-occurring hypersensitivity symptoms (e.g., appearance of a

localized or generalized pruritis within 1 week after treatment), symptomatic treatment may be given (e.g., oral antihistamine, or corticosteroids).

- Please note that late occurring events including isolated fever and fatigue may represent the presentation of systemic inflammation. Please evaluate accordingly.

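### Sections 5.6.2 and 5.6.3 both describe an infusion reaction whose symptoms return after restart: one leaves later dosing open, the other calls it grade 3 and stops nivolumab for good

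*Combined protocol and SAP*

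**What the plan says.** Section 5.6.2 (grade 2) stops the infusion and treats the patient. It continues: "If the infusion is interrupted, then restart the infusion at 50% of the original infusion rate when symptoms resolve". If the symptoms come back, "If symptoms recur, then no further nivolumab will be administered at that visit", and the amount infused is recorded. The same paragraph then turns to later doses: "The following prophylactic premedications are recommended for future infusions: diphenhydramine 50 mg (or equivalent) and (acetaminophen" and so on. It makes no exception there for a patient whose symptoms recurred.

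Section 5.6.3 (grades 3 and 4) includes in its description of grade 3 "recurrence of symptoms following initial improvement; hospitalization indicated for other clinical sequelae". Its instruction is "Nivolumab will be permanently discontinued".

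Section 5.3, item b, states for grade 3 drug-related events that an "infusion reaction of any duration requires discontinuation except as noted in item 'h' below".

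The introduction to 5.6 says that infusion reactions are graded by CTCAE version 4.0 and that the treatment recommendations may be adapted to local standards.

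**The concern.** The recurrence step in 5.6.2 and one of the grade 3 criteria in 5.6.3 describe the same clinical course, but the consequences differ. Under 5.6.2 the infusion ends for that day and later doses remain possible. Under 5.6.3 and 5.3(b) the drug is stopped permanently. In a multicenter trial, two sites could each follow the protocol faithfully, treat the same patient differently and record different grades.

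Three things depend on the answer:

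- whether the patient may receive nivolumab again;
- whether the event is tabulated as severe in the safety analysis;
- if the event is serious, how quickly it must be reported.

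Infusion-related reactions are one of the few event types that 13.4.1 names for follow-up over time, so inconsistent grading would affect a safety result that the trial has singled out.

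**Working it through.** The documents give no figure for this point, so the check sets the texts side by side and follows one patient through them.

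**One patient.** A grade 2 reaction occurs, the infusion is stopped, symptoms resolve, the infusion restarts at 50% of the original rate, and symptoms return.

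| | 5.6.2 | 5.6.3 with 5.3(b) |
|---|---|---|
| Does the patient fit? | Yes: recurrence after restart | Yes: recurrence after improvement |
| Implied grade | 2 (the section is headed grade 2) | 3 |
| Nivolumab that day | No more | No more |
| Nivolumab later | Left open, with premedication | Permanently discontinued |

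**How far the descriptions overlap.** 5.6.2 allows restart only when symptoms resolve. A recurrence after restart therefore always follows improvement. Every patient who reaches the recurrence step of 5.6.2 also meets the 5.6.3 criterion, so the overlap is complete.

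**Does other text settle it?**

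1. *Section 5.3, item h.* Item b is subject to the exceptions in item h. The relevant exception covers short-lived grade 3 drug-related events other than those already dealt with. Infusion reaction is named in item b, so on its natural reading item h does not exempt it.
2. *Section 5.5.1.* The grade 3 events for which restarting is allowed are skin rash and thyroiditis. Infusion reaction is not among them.
3. *Introduction to 5.6.* It names a grading standard and permits local adaptation. It does not say whether 5.6.2 or 5.6.3 governs a recurrence. The permission concerns the treatment recommendations that follow it; 5.3(b) is a discontinuation criterion in another section.

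**What the grade changes.**

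- *Section 13.4.1* records the maximum grade per patient and limits assessment to severe or worse events. Grade 2 or 3 decides entry. The event is still captured as a named event of interest in either case.
- *Section 7.3.3* sets reporting times for serious events. Grades 3 to 5 need a 24-hour notice and a full report within 5 calendar days. Grades 1 and 2 need a report within 10 calendar days if there is hospitalization of at least 24 hours, and none otherwise. Section 7.1 lists no exception to expedited reporting for infusion related reaction. Section 5.6 makes SAE reporting of grade 3 or 4 reactions conditional on the criteria being met, so grade matters here together with seriousness.
- *Section 13.5.2* counts grade 4 and grade 5 events only. A change between grade 2 and grade 3 does not touch the stopping rule.

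**The case against.** **A coherent reading is available.** Each subsection of 5.6 is keyed to grade, and the introduction names CTCAE 4.0. One can say: grade the event first; if the recurrence makes it grade 3, 5.6.3 and 5.3(b) apply, and 5.6.2 covers the event only while it is grade 2. This is reasonable, and many investigators may read it so. It does not remove the conflict, because 5.6.2 itself contains the recurrence step, gives it a same-day consequence, and never points to 5.6.3.

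**5.6.2 does not order re-dosing.** This stands. The same-day wording is a bedside instruction, and the premedication sentence applies most obviously to patients who restart without trouble. A reader might infer that the protocol requires the same patient to be both re-exposed and stopped. The text supports less: later dosing is left open in one place and barred in another.

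**The affected group may be very small.** This also stands. Section 5.2 calls infusion reactions uncommon. A reader might take the Less Likely band in 7.1 (at most 20%, from 2069 patients) as a ceiling of 0.20 × 35 = 7 patients. It is a frequency band, not a cap on this sample: if the true rate were 20%, 7 would be the expected number, and under Binomial(35, 0.20) the chance of more than 7 is 0.40. The band also gives no split by grade or recurrence.

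**Could it change the efficacy verdict?** A reader might note that the final rule needs 4 responders in 35, that at a true response rate of 20% the chance of exactly 4 is C(35,4) × 0.2⁴ × 0.8³¹ = 0.083, and that losing one of them would reverse the conclusion. But 0.083 is only the chance of landing on the boundary. Reversal also needs one of those four to have a recurrent reaction and to lose the response because treatment stopped. Suppose, as an assumption, that 1% to 5% of patients recur, independently of response, and that every such stop forfeits the response. The joint chance is then 0.083 × [1 − (1 − p)⁴], which is 0.3% at p = 1% and 1.5% at p = 5%. Nothing in the documents says that stopping forfeits a response. The efficacy argument is not supported.

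**Conclusion.** The protocol gives incompatible instructions for one defined course: a grade 2 infusion reaction that resolves, is restarted and recurs. The conclusion rests on the wording of 5.6.2, 5.6.3 and 5.3(b), and on reading item h as not covering infusion reactions. The introduction to 5.6 softens the conflict without settling it.

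The consequence is possible inconsistency between sites in grade (2 or 3), in continuation of treatment, in entry to the severe-or-worse assessment and, for serious events, in reporting time. It would be an overstatement to say that grade alone decides expedited reporting, or that the safety stopping rule or the primary response analysis is affected.

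The number of patients concerned cannot be derived from the documents. The correction is worth making because it concerns a discontinuation criterion, and it should be made at the next amendment. This review takes no position on which clinical rule is right.

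**What to change.** Reconcile 5.6.2, 5.6.3 and 5.3(b):

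1. State in one place how a recurrence of symptoms on restart is graded.
2. Make the instruction on later infusions, including the premedication sentence in 5.6.2, follow that grade.
3. Add a cross-reference to 5.6.3 at the recurrence step in 5.6.2.

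The sponsor decides which rule applies. The cost is about one sentence and a cross-reference at the next amendment, with no added patients, tests or analyses.

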5.6.3 For Grade 3 or Grade 4 Symptoms

(Severe reaction), Grade 3 symptoms: prolonged [i.e., not rapidly responsive to symptomatic medication and/or brief interruption of infusion]; recurrence of symptoms following initial improvement; hospitalization indicated for other clinical sequelae [e.g., renal impairment, pulmonary infiltrates]). Grade 4 symptoms: (life threatening; pressor or ventilator support indicated).

Immediately discontinue infusion of nivolumab. Begin an IV infusion of normal saline, and treat the subject as follows. Recommend bronchodilators, epinephrine 0.2 to 1 mg of a 1:1,000 solution for subcutaneous administration or 0.1 to 0.25 mg of a 1:10,000 solution injected slowly for IV administration, and/or diphenhydramine 50 mg IV with methylprednisolone 100 mg IV (or equivalent), as needed. Patient should be monitored until the investigator is comfortable that the symptoms will not recur. Nivolumab will be permanently discontinued. Investigators should follow their institutional guidelines for the treatment of anaphylaxis. Remain at bedside and monitor patient until recovery from symptoms. In the case of late-occurring hypersensitivity symptoms (e.g., appearance of a

localized or generalized pruritis within 1 week after treatment), symptomatic treatment may be given (e.g., oral antihistamine, or corticosteroids).

- Please note that late occurring events including isolated fever and fatigue may represent the presentation of systemic inflammation. Please evaluate accordingly.

5.7 Treatment Beyond Progression

A minority of subjects treated with immunotherapy may derive clinical benefit either delayed responses, stable disease, or increased overall survival despite initial evidence of progressive disease (PD) with nivolumab or combination treatment.

Patients may be permitted to continue treatment beyond initial RECIST 1.1-defined PD occurring during the initial induction period (up to 12 weeks), as long as they meet all of the following criteria (see section 5.7.1 below). Patients are allowed to continue treatment for one additional cycle (4 weeks) and then be reassessed.

5.7.1 Criteria for Continuing Treatment Beyond Progression

- 1) No more than 4 new lesions (excluding new brain metastases), with the total sum of the longest diameter (SHORT diameter for LN) cannot exceed 40% of the initial sum including new lesions
- 2) Patients must be clinically stable with no change in performance status due to disease progression
- 3) No indication for immediate alternative treatment (such as radiotherapy).
- 4) Patient [assessed by the investigator] is showing clinical benefit and tolerates study drug. The assessment of clinical benefit should take into account whether the subject is clinically stable or deteriorating and likely or unlikely to receive further benefit from continued treatment.
- 5) The time of progression is noted from the first assessment that exceeds standard criteria

New lesions are considered measurable at the time of initial progression if the longest diameter is at least 10 mm (except for pathological lymph nodes, which must have a short axis of at least 15 mm). Any new lesion considered non-measurable at the time of initial progression may become measurable and therefore included in the tumor burden measurement if the longest diameter increases to at least 10 mm (except for pathological lymph nodes, which must have an increase in short axis to at least 15 mm).

All decisions to continue treatment beyond initial progression must be documented in the study record and are a part of an agreement with DCTD, NCI.

For statistical analyses: Subjects who continue treatment beyond first progression (as determined by the initial investigator-assessed, RECIST 1.1-defined progression) will be considered to have investigator-assessed ‘progressive disease’ at the time of the initial

progression event. However, if they subsequently experience a CR or PR they may be designated as a ‘delayed response’ for the purposes of determining ORR and thus, in the final analysis, be counted as a responder for the two-stage design.

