11.1 Schedule of Evaluations

For the purposes of this study, patients should be re-evaluated for objective tumor response at week 8 after the first dose of nivolumab, and then at week 16 and week 24, and then every 12 weeks thereafter. In addition to a baseline scan, confirmatory scans should also be obtained within 8 weeks (not less than 4) following initial documentation of objective response.

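### Criterion 1 of section 5.7.1 is misworded: read literally, its 40% limit bars every patient with week-8 progression by target growth from continuing treatment

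*Combined protocol and SAP*

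**What the plan says.** Section 5.3 ends treatment at disease progression "unless the investigator judges that the patient is eligible for continuing beyond progression as stated in section 5.7". Section 5.7 then covers RECIST 1.1 progression "occurring during the initial induction period (up to 12 weeks), as long as they meet all of the following criteria", so the items of section 5.7.1 apply jointly. Criterion 1 allows no more than four new lesions, "with the total sum of the longest diameter (SHORT diameter for LN) cannot exceed 40% of the initial sum including new lesions". Criteria 2 to 4 add clinical stability, no need for immediate alternative treatment, and clinical benefit with tolerance of the drug.

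Section 5.7.1 also says how new lesions are sized: "New lesions are considered measurable at the time of initial progression if the longest diameter is at least 10 mm", with a 15 mm short axis for nodes. A new lesion that is too small at first "may become measurable and therefore included in the tumor burden measurement if the longest diameter increases to at least 10 mm".

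Continuation is limited: "Patients are allowed to continue treatment for one additional cycle (4 weeks) and then be reassessed". Each decision to continue "must be documented in the study record and are a part of an agreement with DCTD, NCI". Scans are scheduled "at week 8 after the first dose of nivolumab, and then at week 16 and week 24" (section 11.1). No other section restates or corrects the 40% limit.

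**The concern.** Section 5.7 exists for patients who may benefit although their disease has met the standard definition of progression. A ceiling of 40% of the initial sum lies far below baseline, whereas progression by target growth lies above it. The words that would make the limit sensible, such as an increase of 40% or 40% above baseline, are absent.

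The limit is a mandatory number governing dosing after progression in a multicenter trial. A site applying the sentence as written must stop patients whom a site reading it as a permitted increase may keep on treatment. Patients who continue are also the ones who may later be designated delayed responders under section 13.1.2, so the criterion helps decide who can reach that category.

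**Working it through.** The 40% is a chosen threshold, not a derived figure, so there is nothing to reproduce. The check is whether it is compatible with the protocol's own definition of progression.

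**Inputs.**
- Ceiling, read literally: total sum, new lesions included, ≤ 0.40 × BSD (5.7.1).
- Progression by target growth: sum ≥ the larger of 1.20 × MSD and MSD + 0.5 cm (11.4.3). MSD is the smallest sum so far, baseline included (11.4.1).
- Progression also follows from a new malignant lesion or unequivocal non-target progression (11.4.3).
- Week 8 is the only routine scan within 12 weeks. A first response at week 8 is rescanned 4 to 8 weeks later, so possibly at week 12 (11.1).

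**Week-8 target growth.** If the sum has grown at the first scan, MSD = BSD. Progression therefore needs at least 1.20 × BSD (a higher percentage if BSD is below 2.5 cm, where the 0.5 cm condition governs). The ceiling is 0.40 × BSD, so no patient can satisfy both. With BSD 10.0 cm: at least 12.0 cm against at most 4.0 cm.

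**Week-8 new lesion or non-target progression.** The total must be ≤ 0.40 × BSD, a net shrinkage of at least 1 − 0.40 = 60%. If measurable new lesions add 10%, 20% or 30% of BSD, targets must be at most 30%, 20% or 10% of BSD, a shrinkage of at least 70%, 80% or 90%.

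**Target growth at a week-12 confirmatory scan.** This can meet the ceiling, but only from a nadir *n* with 1.20*n* ≤ 0.40 × BSD and *n* + 0.5 ≤ 0.40 × BSD. For BSD 10.0 cm, *n* ≤ 3.33 cm (33.3%). For BSD 5.0 cm, *n* ≤ 1.5 cm (30%).

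**The allowance of four new lesions.** Four at the 1.0 cm minimum total 4.0 cm, which uses the whole literal ceiling when BSD is 10.0 cm (4.0/0.40). Four nodes at 1.5 cm total 6.0 cm, which exceeds it whenever BSD is below 15.0 cm (6.0/0.40). At BSD 20.0 cm the ceiling is 8.0 cm, leaving 4.0 cm or 2.0 cm for the targets. How badly the two halves of the criterion clash therefore depends on BSD, and the documents give no expected BSD.

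**Three readings compared.** Let T be the target sum, N the sum of measurable new lesions, and BSD = 10.0 cm. Every row is progression under 11.4.3, and each possible continuation still needs criteria 2 to 4.

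| Patient | Literal: T + N ≤ 4.0 | 40% increase: T + N ≤ 14.0 | New lesions only: N ≤ 4.0 |
|---|---|---|---|
| T 12.5, N 0 | stop | may continue | may continue |
| T 15.0, N 0 | stop | stop | may continue |
| T 9.0, N 4.5 (total 13.5) | stop | may continue | stop |

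Under the 40% increase reading, week-8 growth progression qualifies between 120% and 140% of BSD.

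**The case against.** The strongest reply is that the sentence has another parse. The clause about the sum follows directly on the phrase about new lesions, so it could cap only the summed diameters of those lesions at 40% of the initial sum. That makes the criterion attainable, and with BSD 10.0 cm four minimum-size lesions come to exactly 40%. The parse is grammatically possible, so it would be too strong to say that the text has only one meaning. It fits poorly, though, with a total sum that is said to include new lesions, and it leaves target growth uncapped. As the table shows, it also gives different decisions from both other readings. It narrows the point without removing it.

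It can also be said that 140% of BSD is not in the documents. That is correct: it is inferred from the combined-sum wording, from the purpose of section 5.7, and by analogy with section 11.5, where index and new lesions are added together for the immune criteria.

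Finally, the safeguards are real: one extra cycle and reassessment, three further clinical criteria, and documented decisions. They limit the consequence, but none of them states the threshold, so they do not make sites apply the same one.

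**Conclusion.** Criterion 1 is misworded. On its most natural literal reading it excludes all week-8 progression by target growth and requires at least 60% net shrinkage for the other routes, contrary to the purpose of section 5.7. The week-8 result holds for any BSD, assuming no unscheduled earlier scan has lowered the reference sum; the protocol schedules none. Confidence in the defect is high. Confidence in the intended limit is lower: a 40% increase is the likely meaning, not an established one.

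Two stronger conclusions might be inferred, and the documents support neither. The first is that nobody can continue beyond progression. New-lesion or non-target progression with deep shrinkage can pass, as can growth at week 12 from a nadir of at most a third of BSD. The second is that the wording distorts the response rate or the decision rule of 4 in 35 (section 13.1.4). The delayed-responder designation is permissive, and the documents give neither a split of progression types nor an expected number of delayed responders. No effect on the primary result is shown or can be computed.

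This is a minor correction of a dosing threshold.

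**What to change.** The sponsor and clinical team should first confirm which limit was intended, because a 140% ceiling on the combined sum and a 40% ceiling on new lesions are different rules. Criterion 1 should then be restated with the reference and direction explicit. If the likely intent is confirmed: *at most four new lesions (excluding new brain metastases), and target-lesion plus measurable new-lesion diameters, using the short axis for nodes, together at most 140% of BSD.*

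The cost is one sentence in an amendment. No new data are needed, because target lesions are already measured and new-lesion diameters are already required to apply the criterion. The sample size and decision rules are unchanged.
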